7.3.1 Planned Duration for the Individual Participant

For the individual participants, the core study lasts for a maximum of 184 days. The study duration might be shorter for individual participants in the event that the treatment ceases to be effective.

7.3.2 **Premature Termination**

Study

At any time, the study as a whole will be terminated prematurely by the Sponsor if:

- New toxicological or pharmacological findings or SAEs invalidate the earlier positive benefit—risk assessment
- The development of the study IMP is discontinued, a market authorisation is no longer intended, or the study proves not to meet the expected goal

• Other important reasons, not named above, call for the premature termination of the study

Centre

At any time, an individual centre participating in the study can be excluded from participation by a joint decision between Insuvia UAB, QRCC and the Sponsor if the centre fails to:

- Comply with the requirements of the protocol
- Comply with GCP standards
- Recruit the first participant within a reasonable period

Participant

Individual participants are to be withdrawn from the study according to the criteria specified in Section 4.3.

8 Statistics

8.1 Statistical and Analytical Plans

All statistical analyses will be outlined in detail in a SAP which will be prepared and signed prior to any study-specific analyses. In general, all continuous measures will be summarised descriptively, including number of available values, minimum, Quartiles 1 and 3, median, mean, standard deviation (SD), maximum, and 95% confidence interval (CI) for the mean if appropriate. Categorical data will be presented by frequency and percentage. Ordinal ratings may be handled as continuous data if appropriate. The analysis will be done in 2 stages. Stage 1 will include the analysis of the primary objective: the effect of the loading dose on achievement of castration levels by Day 28 (primary endpoint analysis). Stage 2 will include all other analyses (full analysis).

8.1.1 Analysis Populations

All participants who have received least 1 dose of study medication will be included in the safety analysis (safety population). The efficacy analysis will be performed on an "intention-to-treat (ITT)" basis and a "PP" basis (see definitions below). Participants with major protocol violations will be excluded from the latter. For this purpose, protocol violations that could interfere with the objectives of the study, incorrect concomitant medications or violation of the inclusion/exclusion criteria etc. will be assessed as 'minor' or 'major' in collaboration with the Sponsor. The criteria for this assessment will be defined before analysis. Listings will be prepared to show the eligibility of all participants. These listings will be presented in a Data Review Meeting.

Definition of Analysis Populations:

Population	Description
Screening	All participants who signed the ICF
population	
Safety	All participants who received any dose of the IMP
population	
Intention-to-	All participants included in the safety population for whom the primary
treat (ITT)	endpoint is evaluable
analysis set	•
Per protocol	All participants included in the ITT analysis set who complete the
(PP) analysis set	study without major protocol violation

The primary analysis will be performed on the PP analysis set. In addition, a sensitivity analysis will be performed using the ITT analysis set. All efficacy assessments on the PP analysis set will be repeated for the ITT analysis set.

8.1.2 Adaptive Study Design

In this study the decision of whether or not the treatment regimen for Group 2 will be tested is based on the treatment effect observed in Group 1 on Day 28. If serum T levels at Day 28 are <0.5 ng/mL, the participant is classified as a treatment responder. Participants with serum

T levels at Day 28 of >2 ng/mL will be classified as non-responders. The target group treatment response is 90%.

Enrolment will continue for Group 1 until 20 participants have completed the Day 28 visit with no more than 2 participants being classified as a treatment failure. Treatment failure is defined by a serum T concentration >2 ng/mL at Day 28 or requiring to be withdrawn at any later timepoint during the study.

If 3 or more participants in Group 1 fail treatment then further enrolment into that group will stop due to statistical confidence that a 90% responder rate cannot be achieved with that dosing regimen. All future participants will be enrolled into Group 2.

If in Group 2 at Day 28, a participant's serum T value (as tested by the local laboratory) is >2 ng/mL, the participant will be withdrawn from the study.

If 7 or more participants fail in Group 2 then all further enrolment will be stopped and the study will be terminated.

The planned Group 1 treatment continuation analysis will be described in greater detail in the SAP.

8.1.3 **Primary Efficacy Analysis**

Primary Endpoint

The primary endpoint of the study is the proportion of participants achieving castration level with serum T < 0.5 ng/mL or 1.73 nmol/L at Day 28.

The primary parameter analysis will be performed on the PP analysis set. In addition, a sensitivity analysis will be performed on the ITT analysis set.

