3.1 Core Study

This is an adaptive Phase 2, open-label, multicentre study to evaluate the PK, PD, efficacy and safety of teverelix TFA, a GnRH antagonist in participants with advanced prostate cancer.

For Group 1, it is planned to enrol approximately 24 participants from 3 investigational sites in Lithuania to obtain 20 evaluable participants with prostate advanced cancer. For Group 2, it is planned to enrol approximately 60 participants from up to 7 investigational sites in Lithuania and (potentially) Netherlands/Belgium in order to obtain 50 evaluable participants with advanced prostate cancer, for the assessment of treatment response on Day 28 and throughout the study up to Day 168.

Figure 1 displays the study design.

The study consists of the following periods/visits:

Page 32 of 84

NTEV

Screening Period: Day -6 to -1 **Groups 1 & 2 Treatment Period:**

Stage 1: Loading dose administered at baseline (Day 0) with follow-up visits until Day 28

Stage 2: Maintenance treatment administered every 6 weeks with visits from Day 28 up to Day 168, or until treatment ceases to become effective

Follow-up Visit: 28 days after the last dose of IMP

Group 2 (Stage 3 subjects only) Treatment Period:

Stage 1: Loading dose administered at baseline (Day 0) with follow-up visits until Day 28

Stage 2: Maintenance treatment administered every 6 weeks with visits from Day 28 up to Day 168, or until treatment ceases to become effective

[figure not shown]
Stage 3: Follow up period. Day 203 visit followed by weekly visits until Day 252 or until serum T levels are ≥ 1 ng/mL (local lab result), whichever occurs first Follow-up Visit: Day 259 or ≥ 7 days after serum T levels are ≥ 1 ng/mL (local lab result), whichever occurs first

An overview of the Schedule of Assessments is provided in Section 7.1. After signing the informed consent for the core study, participants will undergo a screening examination within 6 days prior to the administration of teverelix TFA to verify the participants' eligibility, and to document participant characteristics, including medical and surgical history, and disease characteristics.

Table 1 presents the 2 dosing regimens to be evaluated in this study.

Figure 1: Study Design

TEVERELIX IN ADVANCED PROSTATE CANCER PHASE 2 **STUDY PROGRESSION**

ANT-1111-02, Teverelix TFA in Prostate Cancer

FINAL Version 5.0, 31 May 2022

Page 33 of 84

Table 1: Dosing Regimens under Evaluation

_Group	Loading Dose	Maintenance Dose	Dosing Interval

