1	120 mg IM +120 mg SC	120 mg SC	6 weekly
2	180 mg IM +180 mg SC	180 mg SC	6 weekly

IM=intramuscular; SC=subcutaneous

Initially enrolment will open for Group 1 only. If, after Day 28, a participant's serum T value (as tested by the local laboratory on Day 21) is >2 ng/mL, the participant will be withdrawn from the study.

Enrolment will continue for Group 1 until 20 participants have completed the Day 28 visit with no more than 2 participants being classified as a treatment failure. Treatment failure is defined as having a T level >2 ng/mL at Day 28 (as tested by the local laboratory on Day 21) or requiring to be withdrawn at any later timepoint during the study.

If 3 or more participants fail treatment in Group 1 then further enrolment into that group will stop due to statistical confidence that a 90% responder rate cannot be achieved with that dosing regimen. All future participants will be enrolled into Group 2.

If in Group 2 at Day 28, a participant's serum T value (as tested by the local laboratory on Day 21) is >2 ng/mL, the participant will be withdrawn from the study.

If 7 or more participants fail in Group 2 then all further enrolment will be stopped and the study will be terminated.

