After Stage 1, participants in Group 1 will receive a maintenance dose, which will consist of a single 120 mg SC injection administered every 42 days.

[figure not shown]
If the serum T value (measured by the local laboratory) at the Day 35 visit is >2 ng/mL, the participant will be withdrawn from the study.

If 3 or more participants have a total T (local laboratory) value of >2 ng/mL at Day 21 or at any subsequent study visit, the dosing regimen will have failed to meet its 90% efficacy target and, if applicable, further enrolment into Group 1 will cease.

If treatment of Group 1 has been terminated early due to a low therapeutic response rate, recruitment of participants into Group 2 will start.

After Stage 1, participants in Group 2 will receive a maintenance dose, which will consist of a single 180 mg SC injection administered every 42 days.

Page 39 of 84

If the serum T value (measured by the local laboratory) at the Day 21 visit is >2 ng/mL, the participant will be withdrawn from the study.

Participants will have their serum T measured by the local laboratory 1 week prior to each maintenance dose during Stage 2 of the study. If, at any point the local laboratory serum T result is >2 ng/mL the participant will be withdrawn from the study. Local laboratory serum T values ≤ 2 ng/mL allow the subjects to continue in the study.

Table 3 describes the decision-making process for doses participants will receive based on the results of the locally analysed T level from 7 days prior to the scheduled dosing visit.

Table 3: Decision-making in Relation to Serum Testosterone Levels

[T] (ng/mL)	Action Taken	Dose Administered
≤2	Continue in Stage 2	Group 1: Maintenance dose 120 mg
		SC teverelix TFA
		Group 2: Maintenance dose 180 mg
		SC teverelix TFA
>2	Withdrawal from study, safety	None
	follow-up visit	

SC=subcutaneous; T=testosterone; TFA=Trifluoroacetate

Depending on the level of T prior to dosing, a decision will be made regarding whether to continue the participant in the study, request a re-test 7 days prior to the next scheduled dosing visit, or initiate early study withdrawal. If T levels are ≥ 2 ng/mL, the participant will be withdrawn from the study.

In the event that a participant of Group 1 will be continued during Stage 2, each dose will be administered according to Table 4: Testosterone Testing in Groups 1 and 2 every 6 weeks.

Table 4: Testosterone Testing in Groups 1 and 2

Local [T] Testing	Teverelix TFA Dose

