8.1.11 Software used for Statistical Analysis

The SAS® software version 9.2 (SAS® Institute) or higher will be used for the statistical analysis and for the reporting of this study. PK/PD analyses will be performed with Phoenix® WinNonlin® Version 6.3 or higher (Certara L.P).

8.1.12 **Determination of Sample Size**

Initially, since no confirmatory analyses were planned, no sample size calculations were performed. A total of 24 participants was deemed sufficient for 1 treatment group to obtain at least 20 evaluable participants (Day 168 visit completed).

Subsequently the Sponsor undertook a formal sample size calculation so that the Group 2 data could be used to support the dose selection for future Phase 3 clinical trials.

A sample size of 60 has been chosen on clinical grounds. This number gives good power to detect a minimum proportion of 90% subjects achieving castration with central lab serum T <0.5 ng/mL or 1.73 nmol/L at Day 28 from the per protocol population. It is based on the null hypothesis that the true response rate is 74.5%, the average response rate in previous Teverelix trials not achieving 90% response rate. This is tested using a two-sided test with a 5% alpha level against the alternative hypothesis that the response rate is 90%, the minimally clinically relevant response rate. Based on this, fifty participants give power of 80%. Assuming a dropout rate of 16%, sixty patients are recommended.

Sixty patients will ensure acceptable precision for justification for further analysis of this regimen in Phase 3. A true 90% response rate in this instance would give a confidence interval of (79,96) and if 10 subjects drop out, and interval of (78,97). A true 95% response rate with 60 participants would give a confidence interval of (86,99) and if 10 subjects drop out, an interval of (85,99).

8.2 **Data Management**

Data management will be performed using Oracle Clinical Version 3.3 or later running on 2 Microsoft Windows NT servers. Details will be defined in the data management manual, which will be signed by the Sponsor and the Clinical Research Organisation (CRO) prior to start of the data entry.

9 Data Handling and Data Quality Assurance

9.1 **Data Management**

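### Stopping Group 1 at three failures does not deliver the statistical confidence against a 90% response rate that the plan attributes to it

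*Protocol*

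**What the plan says.** The rule appears in Protocol 3.1 ("If 3 or more participants fail treatment in Group 1 then further enrolment into that group will stop due to statistical confidence"), in Protocol 8.1.2 and again in SAP 2.2.1. All three give the same reason, that enrolment will "stop due to statistical confidence that a 90% responder rate cannot be achieved with that dosing regimen".

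Protocol 8.1.2 defines the two outcomes differently:

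- Response: "If serum T levels at Day 28 are <0.5 ng/mL, the participant is classified as a treatment responder".
- Failure: "Treatment failure is defined by a serum T concentration >2 ng/mL at Day 28 or requiring to be withdrawn at any later timepoint".

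Protocol 3.1 adds that the Day 28 failure is judged on the local laboratory sample taken at Day 21. The Synopsis and Protocol 5.5 word the trigger as "If 3 or more participants have a total T (local laboratory) value of >2 ng/mL at Day 21 or at any subsequent study visit". They describe the consequence as a missed 90% efficacy target and make no claim of confidence.

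On size, Protocol 3.1 says "it is planned to enrol approximately 24 participants from 3 investigational sites in Lithuania to obtain 20 evaluable participants". Protocol 8.1.12 says "Initially, since no confirmatory analyses were planned, no sample size calculations were performed". Protocol 8.1.2 promises more: "The planned Group 1 treatment continuation analysis will be described in greater detail in the SAP". SAP 2.2.1 only repeats the sentence, and SAP 5.2 contains no decision rule for Group 1.

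**The concern.** The clause turns an enrolment cut-off into a statement about the true response rate at 120 mg. Such a statement needs a confidence level, and it needs a link between the event counted and the rate it concerns. The plan gives neither.

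At stake is interpretation. The Synopsis refers to Group 2 participants enrolled under protocol version 4.0, so the move to 180 mg has already been made. SAP 4 describes Group 2 as opening only if Group 1 was judged ineffective. A study report could therefore carry the stop forward as statistical evidence that 120 mg falls short of 90%.

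**Working it through.** **The plan's own figure.** There is none for this rule, so nothing can be reproduced. As a check on method, exact Clopper-Pearson limits reproduce the Group 2 intervals in Protocol 8.1.12: 54/60 gives 79–96% and 45/50 gives 78–97%.

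**Inputs.** Boundary: 3 failures (Protocol 3.1, 8.1.2). Target: 90% (8.1.2). Size: 20 evaluable, about 24 enrolled (3.1).

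**Step 1. Failure as the complement of response (failure rate q = 0.10).** This is an assumption; step 3 drops it. The failure count cannot fall, so the chance of having reached 3 by participant n is P(X ≥ 3) at n:

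P(X ≥ 3) = 1 − (1−q)^n − nq(1−q)^(n−1) − [n(n−1)/2]q²(1−q)^(n−2)

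- n = 20: 1 − 0.1216 − 0.2702 − 0.2852 = 0.323
- n = 24: 1 − 0.0798 − 0.2127 − 0.2718 = 0.436

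Exact limits for x successes in n are the 2.5% point of Beta(x, n−x+1) and the 97.5% point of Beta(x+1, n−x). The one-sided upper limit uses the 95% point of Beta(x+1, n−x).

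| Failures / n | Without failure | Two-sided 95% CI | One-sided 95% upper limit |
|---|---|---|---|
| 3/20 | 85.0% | 62.1–96.8% | 95.8% |
| 3/24 | 87.5% | 67.6–97.3% | 96.5% |

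All these limits leave 90% possible.

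**Step 2. What would exclude 90% on the same reading.**

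- n = 20: 5 failures one-sided (P = 0.043 at a true 90%; upper limit 89.6%), or 6 two-sided (CI 45.7–88.1%).
- n = 24: 6 failures one-sided (P = 0.028; upper limit 88.5%), or 7 two-sided (CI 48.9–87.4%).
- Keeping 3 failures: one-sided exclusion holds only if they fall within the first 8 participants (P = 0.038 at 8, 0.053 at 9), and two-sided only within the first 6 (3/6: 11.8–88.2%; 4/7: 18.4–90.1%). The rule has no such limit.

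**Step 3. The rule's own event.** Failure is local T >2 ng/mL or required later withdrawal. Non-response is T ≥0.5 ng/mL at Day 28. A Day 28 value of 1 ng/mL is neither a response nor a failure. Conversely, a Day 28 responder can fail later. The documents give no failure rate for a regimen with 90% response, so a range is assumed:

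| Assumed failure rate | P(≥3), n = 20 | P(≥3), n = 24 |
|---|---|---|
| 3% | 2.1% | 3.4% |
| 5% | 7.5% | 11.6% |
| 7.5% | 18.6% | 26.7% |
| 10% | 32.3% | 43.6% |

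The probability stays below 5% only if the failure rate is at most 4.2% (n = 20) or 3.5% (n = 24).

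**Step 4. From three failures to an enrolment stop.** Failures can arise at the local tests on Days 35, 77, 119 and 161, when recruitment may already be complete. A third failure after that stops nothing. The probabilities above are therefore upper bounds on a false enrolment stop.

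**The case against.** The strongest reply is that this is loose wording rather than a faulty rule. At most 2 failures among 20 means at least 18/20 = 90% without failure, so the cut-off is coherent as a rule on the observed rate. The Synopsis and Protocol 5.5 already express it that way. The inference is also protected: SAP 6 analyses Group 1 separately, SAP 6.8.1 gives its proportion with a Clopper-Pearson interval, and SAP 5.2 rests any test on confidence intervals. No planned analysis uses the stop as evidence.

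Most of this stands, and it is why the point is minor. It does not rescue the clause, because an observed 90% being out of reach is not confidence about the true rate, and three places claim the latter.

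A reader might infer three stronger things that the documents do not support:

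- *That the rule has a 32–44% false-stop rate.* Those figures need failure to be the complement of response, which it is not, and they are upper bounds even then.
- *That the claim is shown to be false on the rule's own event.* If failures above 2 ng/mL were rare enough under a 90% response rate, three of them would be unusual. The documents simply give no such rate.
- *That the cut-off is wrong or Group 2 was opened improperly.* A pragmatic cut-off needs no significance level, and the documents do not report how many failures occurred or when.

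**Conclusion.** The concern holds in a limited form. The plan attributes to the three-failure rule an inferential property that it does not deliver at 20 to 24 participants. On the complement reading, three failures are compatible with a true 90% rate at the conventional 95% level. On the rule's own event, the strength of evidence depends on an unstated failure rate: over assumed rates of 3–10%, the chance of three or more failures is 2.1–32.3% (n = 20) or 3.4–43.6% (n = 24).

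These results assume independent participants with a common failure rate. The defect is an unsupported rationale rather than a miscalculated figure, since no figure is stated. Severity is minor: only the interpretation of 120 mg is affected.

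**What to change.** Keep the 3-failure cut-off. In SAP 2.2.1, and in Protocol 3.1 and 8.1.2 when they are next amended, delete the clause about statistical confidence and put in its place:

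*This is a pragmatic enrolment cut-off (more than 2 failures against a target of at least 18 of 20 evaluable participants without failure). It is not a statistical test and does not by itself show that the T <0.5 ng/mL response rate is below 90%.*

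If probabilities are quoted, use those for 20 participants and label them as upper bounds under assumed failure rates. The 18-of-20 target refers to evaluable participants: with 24 enrolled and 3 failures, 21 can be free of failure. The Synopsis and Protocol 5.5 sentences can stay.

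Base any conclusion about 120 mg on the Group 1 proportion and Clopper-Pearson interval already planned in SAP 6 and 6.8.1. Read the remark in SAP 4 about Group 1 being ineffective in the same way.

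The SAP change must come before database lock (SAP 7.2), and the study report should carry the same reading. SAP 2.2.1 summarises the protocol, so mark the new sentence as a clarification until the protocol follows. Protocol 10.2 reserves amendments for exceptional cases, so this wording does not justify one alone.

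The cost is one sentence in three places, with no change to conduct, sample size, data or analyses. The sponsor gives up only the claim that the stop itself is statistical evidence against 120 mg.

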8.1.4 Secondary Endpoint Analyses

Secondary Endpoints

- 1. Proportion of participants achieving castration level with serum T <0.2 ng/mL at Day 28
- 2. Proportion of participants achieving castration level with serum T < 0.5 ng/mL at Day 42
- 3. Proportion of participants achieving castration level with serum T <0.2 ng/mL at Day 42
- 4. Proportion of participants achieving a T castration rate over 168 days of treatment period

Note: Castration rate is defined as the observed percentage of participants who have T concentrations < 0.5 ng/mL (1.73 nmol/L) at all scheduled visits.

- 5. Proportion of participants achieving profound castration rate (<0.2 ng/mL) over 168 days of treatment period
- 6. Mean time to T levels falling below castration level (<0.5 ng/mL [1.73 nmol/L]) for the first time
- 7. Mean time to (first) overstep of T castration level after achieving castration
- 8. Mean time for serum T levels to be ≥ 0.5 ng/mL after final, Day 168 injection
- 9. Proportion of participants achieving castration level for LH (LH <1.1 U/L) at Day 28
- 10. Proportion of participants with effective LH castration rate over 168 days of treatment period
- 11. Mean time to LH levels falling below castration level (LH <1.1 U/L) for the first time
- 12. Mean time to (first) overstep of LH castration level after achieving castration
- 13. Changes from baseline in PD and PK parameters over time

- 14. Number of participants with a PSA response of ≥50% reduction at the Day 168 visit
- 15. Number of participants with PSA response of ≥80% reduction at the Day 168 visit
- 16. Percent change from baseline in serum PSA concentration at each visit
- 17. Mean serum PSA concentration at each visit
- 18. Mean serum LH concentration at each visit
- 19. Mean serum T concentration at each visit
- 20. Mean serum FSH concentration at each visit

The secondary efficacy parameters will be analysed in an exploratory manner using descriptive statistics.

Secondary efficacy variables will be summarised by number of available values, minimum, Quartiles 1 and 3e, median, mean, SD, maximum, and 95% CI for the mean if appropriate. Categorical data will be presented by frequency and percentage.

These parameters are according to the secondary endpoints:

- Percentage of participants who have T concentrations <0.2 ng/mL at the end of Stage 1 (Day 28)
- Percentage of participants who have T concentrations <0.5 ng/mL and < 0.2 ng/mL at all scheduled visits
- Percentage of participants who have LH concentrations <1.1 U/L at all scheduled visits
- Time to T levels falling below castration level (<0.5 ng/mL) for the first time
- Time to first T concentration ≥0.5 ng/mL after castration has been achieved
- Time to LH levels falling below castration level (<1.1 U/L) for the first time
- Time to first LH concentration ≥1.1 U/L after castration has been achieved
- PD (LH, FSH, PSA, T) and PK (teverelix TFA concentrations) parameters over time (see Sections 6.4 and 6.5) and their changes from baseline
- Serum PSA concentration at each visit including absolute and relative change from baseline
- Number of participants with a PSA response of ≥50% reduction at the Day 168 visit compared to baseline
- Number of participants with a PSA response of ≥90% reduction at the Day 168 visit compared to baseline
- Serum LH concentration at each visit
- Serum FSH concentration at each visit

PK/PD parameters will be analysed by measuring actual times for each concentration. Descriptive statistics will be based on the scheduled times. The participants' concentration-time curves will be presented graphically per parameter.

Further details regarding PK/PD analyses, including scale transformations, parameter formulas and determination of terminal rate will be detailed in the SAP.

